from this study, and design of a large-scale follow up trial to test the effectiveness of the improved intervention.

6. Participant Enrollment and Withdrawal

Participant Inclusion Criteria

Participants will be eligible to participate in the study if they:

- Are 18 years or older
- Have an iPhone or Android phone
- Are a U.S. resident
- Are not in another form of alcohol treatment
- Are actively drinking in the past 3 months
- Have English language proficiency
- Are not using another mHealth alcohol intervention
- Score on the USAUDIT between an 8 to 24 for males under 65
- Score on the USAUDIT between a 7 to 24 for females and males over 65 on the USAUDIT
- Electronically sign the consent form

For the interviews, from back-end data capture we will determine high and low users by the amount of time they spend using the app or the chatbot. High utilizers will be selected from amongst those participants in the top third of each intervention's use (based on total frequency and duration of use) and low utilizers will be selected from those in the bottom third for each intervention. Only participants in either the app or the chatbot intervention groups will be randomly selected to be interviewed.

Participant Exclusion Criteria

Participants will be excluded from participating if they indicate they are:

- more than 30 days abstinent at baseline
- in alcohol or drug abuse treatment currently
- pregnant or nursing
- having a moderate to severe level of alcohol use disorder, defined as having a score of 25 or higher on the USAUDIT
- unwilling or unable to complete follow-up assessment
- not residents of the U.S.
- unable to read or text in English

Recruitment and Enrollment

Participant recruitment will be conducted through Facebook advertisements. The advertisements will provide a link to the study website which will describe the study and provide a link to the prescreen survey. Facebook analytics will be reviewed weekly by the graduate research assistant and project manager. Analytics will be reviewed on each of the ads for which ads are more successful at recruiting interested participants and the demographics the ads are more successful at recruiting. These analytics will inform how to alter advertisements if the sample being recruited is largely one race or gender. Recruitment will begin in June 2020 and will end when the target sample is reached.

Prescreen

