A prescreen survey will be hosted through Qualtrics. It will survey for eligibility criteria which includes demographic questions and the US AUDIT screening questionnaire. Participants will be automatically directed to the consent form hosted on Qualtrics if they are eligible. They will automatically be directed to a debriefing screen and resources if they are not eligible. The AUDIT is the most widely used alcohol screening test in the world with more than 25 years of validation studies worldwide. We will use the USAUDIT, a recent adaptation of the original AUDIT that uses U.S. standard drink amounts and NIAAA drink limits. A score of 8 or greater on the USAUDIT suggests that they are at risk of experiencing significant problems from drinking alcohol. This cut point has been found to yield high sensitivity and specificity when compared to a number of criteria for problematic alcohol use (e.g., alcohol dependence); thus, numerous studies have found it to be an accurate screening tool for alcohol problems among numerous groups including women and older adults. In the current study, the standard cut point of 8 for men and 6 for women and men over 65 will be used to establish problem drinking. Participants with high likelihood of alcohol dependence, evidenced by a score of 25 or above will be screened out of the study.

Target Sample Size

The target sample size is a minimum of 50 participants per intervention arm (i.e., app group, chatbot group, delay group). This will provide adequate power to detect modest effect sizes, pre to post, in outcomes for pilot purposes. For the interviews, 20 participants (10 from the app group and 10 from the chatbot group) will be randomly selected and asked to participate.

Participant Withdrawal or Termination

Participants are free to withdraw from participation in the study at any time upon request. An investigator may terminate participation in the study if the participant meets an exclusion criterion (either newly developed or not previously recognized) that precludes further study participation.

7. Study Procedures and Schedule

This study will consist of three phases. Phase I will focus on developing the AI chatbot version of Step Away and developing procedures for the pilot study, including evaluating the different program elements using an expert panel.

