Phase II will entail a feasibility study that will contrast the Step Away chatbot with the Step Away app and a wait-list control condition, utilizing a randomized, controlled study design. A face-to-face control condition will not be utilized in this study as research has indicated that mobile health apps reach a different population of potential users whom we want to recruit for this study. A minimum of one hundred and fifty participants who are 18 years of age and older who screen positive for unhealthy alcohol use will be recruited throughout the U.S. with Facebook advertisements. All participants will complete an online, baseline research assessment and a follow-up at 4 months, allowing a minimum of 3 months of intervention use. Three months of intervention use will allow enough time for participants to utilize all aspects of the intervention system (the set-up phase), extended exposure to the daily assessment and weekly feedback functionality and provide a mid-length follow up period. Data from the app and chatbot usage will be continually uploaded to a secure server to determine usage and treatment fidelity information for each intervention. In addition, 10 participants in the chatbot and app conditions will be interviewed based on their degree of engagement with each intervention to obtain their perspectives on each intervention's usefulness and barriers to engagement. (At the 4-month

follow-up, all participants will be given the Substance Abuse and Mental Health Services Administration's (SAMHSA) national treatment locator helpline to identify treatment services in their area.)

Phase III will focus on quantitative and qualitative data analysis, manuscript development, conference presentations and preparation of a large-scale follow up grant.

All screening, baseline, and follow-up assessments will be performed online through Qualtrics.

Screening

All participants will be screened for eligibility. A copy of the screening questionnaire is available in the appendix.

Baseline

- The Timeline Followback (TLFB) will be used to gather information on alcohol and drug use. The TLFB will be used to calculate the following drinking variables: average (mean) drinks per week, days abstinent, and heavy drinking days. Heavy drinking days will be defined as days with 4 or more standard drinks for women and 5 or more standard drinks for men.
- Short Inventory of Problems – Revised (SIP-R) will be used to assess the adverse consequences of substance use.

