- The treatment history section of the Form 90 will be modified to be administered online at baseline and follow-up, to gather lifetime treatment history, self-help attendance, and treatment use.
- Readiness to Change. We will utilize the Readiness to Change Treatment Version (RCQTV), which RCQTV has been shown to have solid reliability and validity and has been modified for individuals contemplating or engaged in treatment for alcohol problems.

Follow-Up

The US AUDIT, TLFB, SIP-R, and Readiness to Change questionnaires will be used for the follow-up assessments. In addition, those in the app and chatbot groups will be asked to complete the System Usability Scale to assess their perceptions of the interventions' usability. The follow-up survey will be sent to participants at 4 months post-enrollment.

Interviews

Interviews will be conducted after the completion of the follow-up survey. Interview questionnaires will focus on users' experiences with the app or the chatbot. These interviews will be conducted over the phone.

8. Assessment of Safety

Several safety measures will be put in place to ensure the safety, comfort, and confidentiality of all participants. Care will be taken to inform potential participants fully before they consent to participate about all potential risks that may arise from their participation. The two most important aspects of participant protection in the proposed work are assuring the adequacy of informed consent (including full disclosure of all potential risks) and protecting confidentiality. To minimize risk, we will clearly explain all procedures to participants in our informed consent documents and clearly outline safeguards for confidentiality implemented in the study. Further, in order to protect their confidentiality, all participants will be encouraged to set a password to access their smartphone home screen.

Also, a Data Safety Monitoring Board (DSMB) will be convened in Year 1 of the project and will include the following two members with expertise in psychology, behavioral health, and

research ethics. The DSMB will meet twice during each year of the project to review the status of the project.

9. Statistical Considerations

All randomized study participants who complete both the baseline and follow-up surveys will be the primary population for the analysis. Three subgroups will be analyzed: the app group, the chatbot group, and the delay group.

Outcomes, Statistical Methods, and Statistical Analyses

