Consent and Other Informational Documents Provided to Participants

Copies of the consent documents, emails, and other outreach to participants are provided in the Appendix.

Consent Procedures and Documentation

A brief overview will tell participants who is conducting the research study, and that it involves trying out a program to address unhealthy alcohol use that involves a program delivered over their smartphone. They will be told that if they want to join the study they will be placed in one of three groups, and that all groups will be of no cost to them and that all programs will also ask them to do activities on their phone to help them manage their drinking. Also, they will be told that no matter which group they are in, they will be asked to complete electronic surveys two times during the study and will possibly be asked to participate in a short interview at the end of the study. They will also be informed that [name] has a financial interest in the company, Here and Now Systems, LLC that owns the Step Away intervention and that results may inform future versions as commercial products. They will be informed that [name] will not be involved in data management and analysis within this study and that those procedures will be performed by the UAA Center for Behavioral Health Research and Services (CBHRS) under the supervision of [name]. They would then be asked to click ‘yes’ if they are interested and would like to be screened to see if the study is right for them. If they assent to be screened,

they will be first told that all information they provide will be kept private, and that they can exit at any time. They will then electronically be asked all screening questions and an eligibility determination will be made and communicated to them. Those who are ineligible or who decide not to participate will be offered referrals to other substance abuse treatment services in the community.

Eligible and interested participants will then undergo an electronic informed consent (eIC) process, following guidance for Institutional Review Boards, Investigators, and Sponsors, described in a 2016 Procedural co-authored by the US Department of Health and Human Services (DHHS), Office for Human Research Protections (OHRP), Center for Drug Evaluation and Research, and other federal agencies (www.fda.gov/downloads/drugs/guidances/ucm436811.pdf).

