If yes: Do you have a few more minutes to stay on the line while I call for services in our area with you?

If yes: call [name] and begin warm handoff (ask them what state they are from)

Hi, my name is ____ and I'm a researcher on a current alcohol study. I have ____ (name of participant) here on the phone line with me and they are interested in finding services in ____ (their state). Can you help connect them?

If no: What email would you like me to send the resources to?
(findtreatment.gov/ or call [[name]]([contact]))

The last few questions are about how you have been feeling over the past two weeks.

1. How often have you been bothered by feeling down, depressed, or hopeless?
 - (0) Not at all
 - (1) Several days
 - (2) More than half the days
 - (3) Nearly every day
2. I am going to read some statements to you. Please tell me which statement best describes how you have been feeling over the past two weeks.
 - (0) I do not feel sad
 - (1) I feel sad
 - (2) I am sad all the time and I can't snap out of it
 - (3) I am so sad and unhappy that I can't stand it
3.
 - (0) I am not particularly discouraged about the future
 - (1) I feel discouraged about the future
 - (2) I feel I have nothing to look forward to
 - (3) I feel the future is hopeless and that things cannot improve

If 5 or higher:

Have the symptoms I just asked about gotten worse over the past two weeks?

If yes: Do you believe the Step Away app is contributing to your increased level of distress?

If yes: It sounds like this study is not a good fit for you. You may delete the app and discontinue using it. [*Continue with resources*].

All positives: Based on your answers you may benefit from discussing these issues further. I'm going to send you some phone numbers, where you can either text or call to talk to someone with experience discussing these issues.

Is that OK? (wait for response before moving on)

You may also text "MHA" to [name] to speak with a professional via text.

If you are feeling distressed and wish to talk over the phone, you may call the National Suicide Prevention Hotline at [name]. They also have a live online chat at suicidepreventionlifeline.org.

What email would you like me to send these resources to?

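### Minor wording point: one line of the check-in script says the study does not suit the participant when only the app is being stopped, and the 4-month survey is still due

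*Combined protocol and SAP*

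**What the plan says.** The appendix call script ends with three mood items, each scored 0 to 3. At a total of 5 or higher the caller asks whether the symptoms have worsened over the past two weeks. If so, the caller asks: "Do you believe the Step Away app is contributing to your increased level of distress". If the answer is yes, the caller says: "It sounds like this study is not a good fit for you. You may delete the app and discontinue using it", and goes on to the help resources.

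Other parts of the document bear on what this person still owes the study:

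- Section 7 (Study Procedures and Schedule): "All participants will complete an online, baseline research assessment and a follow-up at 4 months".
- Section 7, Follow-Up: "The follow-up survey will be sent to participants at 4 months post-enrollment". No condition on product use is attached.
- Section 10, Consent Procedures and Documentation, says participants are told that "no matter which group they are in, they will be asked to complete electronic surveys two times during the study".
- Section 6, Participant Withdrawal or Termination: "Participants are free to withdraw from participation in the study at any time upon request". An investigator may also end participation if an exclusion criterion is met. Low mood and distress are not on the exclusion list in the same section.
- Section 9 (Statistical Considerations): "All randomized study participants who complete both the baseline and follow-up surveys will be the primary population for the analysis".

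**The concern.** Stopping an intervention and leaving a trial are different events, and this line runs them together. The participant has not asked to withdraw and meets no listed ground for termination, yet hears that the study is not for them. The visible script does not add that they remain enrolled or that a survey will follow. The call also opens by asking how taking part in the study has been going, so the listener has already been given that word as the name of the whole undertaking.

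The group who hear the line is a selected one: they say the product made them feel worse. Because the primary population is defined by survey completion, anyone who takes the line as dismissal and does not respond drops out of the primary analysis for a reason connected with a bad reaction to the product. Psychiatric worsening is a risk that Section 3 names. The usability rating, which is collected at follow-up in the app and chatbot groups only, would be lost as well.

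**Working it through.** The plan gives no figure on this point, so there is none to reproduce. The check has two parts.

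**1. Does the protocol release this participant from follow-up?**

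- Follow-up: Section 7 asks it of all participants, and the survey is sent by time since enrollment, not by product use.
- Withdrawal: Section 6 allows it on the participant's request. The script records no such request.
- Termination: Section 6 ties it to an exclusion criterion, and distress is not one.

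So under the visible text the survey is still due. If the line was meant as withdrawal, no stated rule supports it. If it was meant as stopping the app, it uses the wrong word.

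**2. How large could the effect be?**

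*Reaching the line.* Three conditions must all hold. The score alone does not need extreme answers throughout: the top answer on the first item and the lowest non-zero answer on the other two gives 3 + 1 + 1 = 5, out of a maximum of 9. The worsening and attribution conditions narrow the group further.

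*Inputs.* The target is at least 50 per arm (Section 6, Target Sample Size). The rest are assumptions, because the documents give no values:

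- k = 1 to 3 people in an arm hear the line and skip the survey because of it, which is 1/50 = 2% to 3/50 = 6% of the arm;
- their drinking change would have been d = 0, 0.5 or 1 SD worse than that of completers;
- two-sided alpha is 0.05 and the SD of change is 1.

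*Shift in the completer mean* = (k/50) × d.

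*Effect on the planned test.* With two time points, the time-by-group F test of Section 9 is the same as a one-way F test on change scores across the three groups. With arm sizes n_i, completer means m_i and overall mean m, its noncentrality is the sum of n_i × (m_i − m)². When one arm is shifted by s and there is no true difference, this reduces to [100 × (50 − k)/(150 − k)] × s². For k = 3 and d = 1: (100 × 47/147) × 0.06² = 0.115.

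| k | d (SD) | Shift (SD) | Type I error, loss in one arm |
|---|---|---|---|
| 1 | 0 | 0 | 0.0500 |
| 1 | 0.5 | 0.01 | 0.0502 |
| 1 | 1 | 0.02 | 0.0510 |
| 3 | 0 | 0 | 0.0500 |
| 3 | 0.5 | 0.03 | 0.0521 |
| 3 | 1 | 0.06 | 0.0586 |

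A simulation of 200,000 trials for the last row gave 0.0583.

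*Variations on the worst row.*

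- The same loss in both active arms gives 0.0587.
- The same loss in all three arms cancels and gives 0.0500.
- If the 191 surveys mentioned under Data Handling and Record Keeping mean about 64 per arm (191/3, an assumption), the shift is 3/64 = 0.047 SD and the type I error 0.0568.

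*Power.* For a pairwise comparison at a standardised difference of 0.5, power is 70.5% with 50 per arm and 68.8% with 48. A few losses cost little precision. What matters is who is lost.

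**The case against.** The strongest reply is that the consequence is speculative. No part of the document says how many people reach this line, how many would skip a survey months later because of one sentence, or how their drinking would differ. Section 3 reports no adverse events in earlier studies of the product, which points to the low end of the assumed range or to zero. The survey is sent to participants regardless of app use, participants were told at the outset to expect two, and nothing in the script cancels the survey or tells staff to stop contact. A later invitation would itself signal that participation continues. Much of the outreach appendix is not visible, including the start of the call procedure, so reminders that would recover these people may exist. Finally, offering someone who is getting worse an easy exit and moving straight to resources is a defensible safety choice.

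Most of this stands, and it sets the severity. It does not remove the mismatch: whatever other outreach exists, this participant is told at this moment that the study does not suit them.

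Three stronger readings should be resisted:

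- **That the script withdraws distressed participants.** It does not. It names no withdrawal step, and people who score 5 or more without both other conditions never hear the line.
- **That the arm comparison is biased.** The visible text does not show whether the loss would differ by arm. Equal loss with equal outcomes cancels.
- **That the safety handling is at fault.** Advising the person to stop the product and offering resources is sound.

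**Conclusion.** The point holds as a minor wording fault. For participants who meet all three conditions, the line describes leaving the study when the protocol supports only stopping the app, and the completer-based primary population makes a resulting missed survey informative. The number affected is unknown and probably very small. Even at the top of the assumed range the completer mean moves by 0.06 SD and type I error stays below 0.06, and the bias in the arm comparison may be zero. All of these sizes rest on assumed counts and differences, not on figures in the plan. The trial's conclusion is not threatened. The reason to act is that the loss is avoidable at almost no cost. Severity: optional.

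**What to change.** Replace the line with wording such as: *The app may not be a good fit for you. You may delete it and stop using it. We would still like to send you the 4-month survey, whether or not you use the app; taking part is your choice and you may leave the study at any time.* Keep the resources step that follows. If the call record does not already do so (the form is not visible), record product discontinuation separately from study withdrawal, so that a missing survey can later be interpreted.

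The cost is two reworded sentences, one added sentence, possibly one record field, and a short IRB amendment. No new contacts are needed, since the survey already goes to everyone. The one real downside is that a distressed participant might feel pressed to stay, which is why the reminder that taking part is voluntary belongs in the line itself.
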